4 STUDY OBJECTIVES

4.1 Primary Objective

Parts 1 and 2: To evaluate the safety and tolerability of VX-659 in triple combination (TC) with tezacaftor (TEZ) and ivacaftor (IVA)

Part 3 (optional): To evaluate the safety and tolerability of VX-659 in TC with TEZ and VX-561 (also known as CTP-656, deuterated IVA)

All parts: To evaluate the efficacy of VX-659 in TC with TEZ and either IVA or VX-561

4.2 Secondary Objectives

Parts 1 and 2: To evaluate the pharmacodynamic (PD) effects of VX-659 in TC with TEZ and IVA on CFTR function

Part 3 (optional): To evaluate the PD effects of VX-659 in TC with TEZ and VX-561 on CFTR function

All parts:

- To evaluate the pharmacokinetics (PK) of VX-659 when administered in TC with TEZ and either IVA or VX-561
- To evaluate the PK of TEZ, IVA, VX-561 and their respective metabolites when administered with VX-659 (as applicable)

5 STUDY ENDPOINTS

5.1 Efficacy Endpoint

5.1.1 Primary Efficacy Endpoint

- Absolute change in percent predicted forced expiratory volume in 1 second (ppFEV₁) from baseline through the Day 29 Visit

5.1.2 Secondary Efficacy Endpoints

- Absolute change in sweat chloride concentrations from baseline through the Day 29 Visit
- Relative change in ppFEV₁ from baseline through the Day 29 Visit
- Absolute change in Cystic Fibrosis Questionnaire-Revised (CFQ-R) respiratory domain score from baseline at the Day 29 Visit

5.2 Safety Endpoints

Safety and tolerability will be evaluated via the following endpoints:

- Adverse events (AEs)
- Clinical laboratory values
- Standard 12-lead ECGs
- Vital signs
- Pulse oximetry
- Spirometry

6 STUDY DESIGN

6.1 Overall Design

This is a Phase 2, randomized, double-blind, placebo- and TEZ/IVA-controlled, parallel-group, 3-part, multicenter study. All parts will be conducted concurrently. Subjects may not participate in more than 1 part.

Key study elements of each part are summarized in [Table 6-1](#), treatment arms and planned doses are shown in [Table 6-2](#), and a schematic of the study design is shown in [Figure 6-1](#). Study visits and assessments are shown in [Table 11-1](#) (Part 1), [Table 11-2](#) (Part 2), and [Table 11-3](#) (Part 3).

Table 6-1 Key Study Elements by Part

Element	Part 1	Part 2	Part 3 (optional)
Study population			
Genotype(s)	F/MF	F/F	F/MF
Age	≥18 years	≥18 years	≥18 years
ppFEV ₁ criteria	≥40 to ≤90	≥40 to ≤90	≥40 to ≤90
Number of subjects	Approximately 54	Approximately 27	Approximately 24
Randomization			
Ratio	1:1:2:2 (placebo:TC-low:TC-mid:TC-high)	1:2 (TEZ/IVA:TC-high)	1:3 (placebo:TC2-high)
Stratification	ppFEV ₁ (<70, ≥70)	ppFEV ₁ (<70, ≥70)	ppFEV ₁ (<70, ≥70)

Table 6-1 Key Study Elements by Part

Element	Part 1	Part 2	Part 3 (optional)
Study design	Parallel group	Parallel group	Parallel group
Control	Placebo	TEZ/IVA	Placebo

F/F: homozygous for *F508del*; F/MF: heterozygous for *F508del* and a minimal *CFTR* function mutation that is not expected to respond to TEZ, IVA, or TEZ/IVA; IVA: ivacaftor; ppFEV₁: percent predicted forced expiratory volume in 1 second; TC: triple combination; TEZ: tezacaftor

Table 6-2 Treatment Arms and Planned Doses by Part

[figure not shown]
	Period 1			Period 2	
	VX-659 Dosage	TEZ Dosage	IVA Dosage	TEZ Dosage	IVA Dosage
Part 1					
TC-high	400 mg qd	100 mg qd	150 mg q12h	100 mg qd	150 mg q12h
TC-mid	240 mg qd	100 mg qd	150 mg q12h	100 mg qd	150 mg q12h
TC-low	80 mg qd	100 mg qd	150 mg q12h	100 mg qd	150 mg q12h
Triple placebo	Placebo	Placebo	Placebo	Placebo	Placebo
Part 2^a					
TEZ/IVA	Placebo	100 mg qd	150 mg q12h	100 mg qd	150 mg q12h
TC-high	400 mg qd	100 mg qd	150 mg q12h	100 mg qd	150 mg q12h
Part 3 (optional)					
	VX-659 Dosage	Period 1		VX-561 Dosage	
		TEZ Dosage			
TC2-high	400 mg qd	100 mg qd		200 mg qd	
Triple placebo	Placebo	Placebo		Placebo	

IVA: ivacaftor; q12h: every 12 hours; qd: daily; TC: triple combination; TEZ: tezacaftor

[figure not shown]
^a In Part 2, all subjects will also receive TEZ 100 mg qd/IVA 150 mg q12h during the Run-in Period

Figure 6-1 Schematic of Study Design

[figure not shown]
Part 1: Subjects With F/MF Genotypes

Part 2: Subjects With F/F Genotype

Part 3: Subjects with F/MF Genotypes (optional)

F/F: homozygous for *F508del*; F/MF: heterozygous for *F508del* and a minimal *CFTR* function mutation that is not expected to respond to TEZ, IVA, or TEZ/IVA; IVA: ivacaftor; N: number of subjects; TEZ: tezacaftor; TC: triple combination

Note: To maintain the blind, matching placebo tablets will be administered, as applicable, so that all subjects receive the same number of tablets within a given dosing period.

6.2 Sample Size and Power

6.2.1 Primary Objectives

The primary objectives of the study are the evaluation of safety and tolerability, and efficacy of VX-659 in TC with TEZ and either IVA or VX-561. The sample size calculations described below are deemed adequate to evaluate the objectives of the study, based on clinical and statistical considerations.

6.2.1.1 Safety and Tolerability

The primary safety endpoint is the incidence of AEs. Approximately 105 subjects will be randomized in the study with approximately 81 subjects receiving VX-659 in TC. The sample size for each treatment group will provide sufficient data for a descriptive analysis of AEs.

6.2.1.2 Efficacy

The primary efficacy endpoint is the absolute change from baseline in ppFEV₁ through the Day 29 Visit in all parts. A sample size of 18 subjects per treatment group provides at least 90% power to detect a mean within-group change of 7 percentage points.

6.2.2 Secondary Objectives

A secondary objective of the study is the evaluation of the PD effect of VX-659 in TC with TEZ and either IVA or VX-561.

The absolute change from baseline through the Day 29 Visit in sweat chloride concentrations is a secondary endpoint used to evaluate the PD objective of the study. In Part 1, a test for a decreasing dose-response trend between placebo and the TC dose groups will be performed using a multiple comparisons procedure (MCP). The procedure consists of testing the null hypothesis of the lack of a decreasing dose-response trend versus a decreasing trend using the 1-sided maximum *t*-statistic that controls the type I error at alpha = 5%. The procedure requires a family of candidate dose-response models to be prespecified, that covers the range of plausible and diverse dose-response profiles.

6.3 Randomization

For all parts, randomization will be stratified by ppFEV₁ values (<70 vs ≥70).

For subjects in Part 1 and Part 3, the spirometry assessment used for stratification must be performed at least 14 days after the last dose of any previous CFTR modulator treatment. Therefore, subjects being treated with 1 or more CFTR modulators (investigational or approved) within 14 days of the Screening Visit must have a separate Stratification Visit at least 14 days after the subject's last CFTR modulator dose. For subjects not being treated with any CFTR modulators within 14 days of the Screening Visit, the Screening Visit spirometry assessment can be used for stratification.

For subjects in Part 2, the ppFEV₁ assessment for stratification of randomization will be done at the Day -14 Visit. See Section 9.3.1 of the protocol.

Randomization will occur before the first dose of VX-659/control and may be done on either Day -1 or the Day 1 Visit, after all inclusion and exclusion criteria have been satisfied and the criteria for entry into the Treatment Period have been confirmed (see Section 9.1.4 of the protocol).

For Part 2, subjects who prematurely discontinue TEZ/IVA during the Run-in Period will not be randomized or participate in the Treatment Period, unless they rescreen and complete a 4-week Run-in Period (Section 9.1.2 of the protocol).

6.4 Blinding and Unblinding

6.4.1 Blinding

This will be a double-blind study.

6.4.2 Blinding

All subjects, site personnel (including the investigator, the site monitor, and the study team), and the Vertex study team will be blinded to the treatment codes with the exception of the following:

- Any site personnel for whom this information is important to ensure the safety of the subject in the event of a life-threatening medical emergency
- Any site personnel for whom this information is important to ensure the safety of the subject and her fetus in the event of a pregnancy
- Vertex Global Patient Safety (GPS) and Regulatory Affairs personnel to satisfy serious adverse event (SAE) processing and reporting regulations
- Unblinded statistician preparing the final (production) randomization list who is not part of the study team
- Vertex IWRS Manager
- Vertex Clinical Supply Chain
- Independent Data Monitoring Committee (IDMC)
- Vendor performing the interim analyses (IAs) and preparing the unblinded analysis for the ongoing reviews of efficacy and safety data, and the IDMC

- Bioanalytical contract research organization (CRO) analyzing PK samples and Vertex Bioanalytical personnel who are not members of the study team may review raw data from Bioanalytical CRO.
- Vertex Modeling and Simulation personnel or vendor conducting the population PK and PK/PD analyses
- Vertex medical monitor may, for matters relating to safety concerns, unblind individual subjects at any time

Blinding of Sweat Chloride and Spirometry Results:

- The Vertex study team will not have access to sweat chloride or spirometry results after a subject receives the first dose of study drug on the Day 1 Visit until after the data are unblinded for full review per Section 12.3.6.1 of the protocol.
- Sites, subjects, and their parents/caregivers/companions should not be informed of a subject's study-related sweat chloride results until after the subject's last study visit, even if the subject prematurely discontinues treatment.
- Subjects and their parents/caregivers/companions should not be informed of the subject's study-related spirometry results until after the subject's last study visit, even if the subject prematurely discontinues treatment.

6.4.3 Unblinding

At the initiation of the study, the study site will be instructed on the method for breaking the blind. The unblinding method will be either a manual or electronic process.

Unblinding of Individual Subject Treatment Assignments by Investigator for Medical Emergencies or Urgent Clinical Situations

Unblinding of the individual subject's treatment by the investigator will be limited to medical emergencies or urgent clinical situations in which knowledge of the subject's study treatment is necessary for clinical management. In such cases, investigators will use their best judgment as to whether to unblind without first attempting to contact the medical monitor to discuss and agree to the need for unblinding. If investigators deem it not necessary to unblind immediately, they will first attempt to contact the medical monitor to discuss and agree to the need for unblinding. If investigators have tried but are unable to reach the medical monitor, they will use their best judgment, based on the nature and urgency of the clinical situation, and may proceed with unblinding without having successfully reached and discussed the situation with the medical monitor.

Contact information for the medical monitor (or appropriate backup) will be provided in a separate document.

In addition, the Vertex Medical Information Call Center [REDACTED] will answer calls 24 hours a day, 7 days a week, 365 days of the year, and will triage these calls to the study medical monitor or appropriate backup.

If a subject's treatment assignment has been unblinded for a medical emergency or urgent clinical situation, the medical monitor will be notified within 24 hours of the unblinding event. The reason and the date of the unblinding will be documented clearly in the subject's study file.

Information about the treatment assignment obtained from the unblinding will be maintained in a secure location with controlled access and will not be shared with the sponsor (Vertex), CRO, or any site personnel (other than the physician treating the subject). In addition, the investigator will consider whether the clinical event that prompted unblinding will be considered an SAE, according to the regulatory definitions or criteria for SAEs, and if so, submit an SAE report to Vertex GPS or designee, per Section 13.1.2 of the protocol.

Unblinding of Individual Subject Treatment Assignments by Vertex GPS or Designee for SAEs or Safety Concerns

Vertex GPS or designee will unblind any SAE reports in compliance with regulatory reporting requirements. In addition, Vertex may, for matters relating to safety concerns, unblind individual subjects at any time.

Unblinded Reviews of Data by Vertex for Administrative Purposes (Planning, Decision-making, and Regulatory Submission)

A limited Vertex team will be unblinded and have access to safety, efficacy, and PD data for the purpose of conducting ongoing reviews of safety and efficacy data for planning and enabling clinical development. Members of the limited unblinded Vertex team will not be part of the Vertex study team and will not be involved in or influence the conduct of the study.

Unblinding: Interim Analysis Results

Interim analyses (IAs) may be conducted for any part of the study after at least 50% of subjects in the part have completed the Day 15 Visit (see Section 12.3.6.1 of the protocol). Each IA will only include data for a single part of the study. The results of these analyses will be reviewed by a limited Vertex team. When an IA is performed after all subjects in a part have completed the Safety Follow-up Visit, results from that part will be unblinded for full review by the Vertex study team.

7 ANALYSIS SETS

The following analysis sets are defined: All Subjects Set, Full Analysis Set and Safety Set.

7.1 All Subjects Set

The **All Subjects Set** will include all subjects who were randomized or received at least 1 dose of study drug. This analysis set will be used for all individual subject data listings and disposition summary tables, unless otherwise specified.

7.2 Full Analysis Set

The **Full Analysis Set** (FAS) will be defined as all randomized subjects who carry the intended CFTR allele mutation and have received at least 1 dose of study drug in Period 1. The FAS will be used to summarize subject demographics and baseline characteristics, and for all PD and efficacy analyses, unless specified otherwise. Subjects will be analyzed according to the treatment they were randomized to.

7.3 Safety Set

7.3.1 Parts 1 and 3

The **Safety Set** will include all subjects who received at least 1 dose of study drug in the Treatment Period. The Safety Set will be used for all safety analyses, unless otherwise specified. Subjects will be analyzed according to the treatment they received.

If a subject received at least 1 dose of a higher TC treatment group, the subject will be analyzed in the higher dose TC treatment group (in increasing priority order of triple placebo, TC-low, TC-mid, and TC-high or TC2-high).

7.3.2 Part 2

The **Safety Set for the Run-in Period** will include all subjects who received at least 1 dose of TEZ/IVA in the Run-in Period. This Safety Set will be used for individual subject data listings for the Run-in Period, unless specified otherwise.

The **Safety Set for the Treatment Period** will include all subjects who received at least 1 dose of study drug in Period 1 of the Treatment Period. This Safety Set will be used for all safety analyses for the Treatment Period, unless specified otherwise.

If a subject received at least 1 dose of a higher TC treatment group, the subject will be analyzed in the higher dose TC treatment group (in increasing priority order of TEZ/IVA and TC-high).

Note: The safety analysis will focus on the Safety Set for the Treatment Period only, unless otherwise specified.

8 STATISTICAL ANALYSIS

8.1 General Considerations

The analysis will be performed for each part, and presented by treatment group and overall, for the Treatment Period, unless specified otherwise. The treatment groups are defined as follows:

- Part 1: *F508del*/MF genotype group
 - Placebo, TC-low, TC-mid, and TC-high.
- Part 2: *F508del*/*F508del* genotype group
 - TEZ/IVA and TC-high.
- Part 3: *F508del*/MF genotype group
 - Placebo and TC2-high.

The Schedule of Assessments is provided in [Appendix A](#). The precision standards for reporting safety and efficacy variables are provided in an internal Biometrics document that specifies the programming rules including the precision for derived variables.

All individual subject data for those randomized or dosed with any amount of study drug will be presented in data listings.

Continuous variables will be summarized using the following descriptive summary statistics: the number of subjects (n), mean, SD, standard error (SE), median, minimum value (min), and maximum value (max). SE may not be reported for safety summary tables.

Categorical variables will be summarized using counts and percentages. Percentages will be presented to 1 decimal place.

Baseline value, unless otherwise specified, will be defined as the most recent non-missing measurement (scheduled or unscheduled) collected before the first dose of study drug on Day 1 of the Treatment Period. For ECG, baseline will be defined as the most recent non-missing measurement (or the average of triplicate measurements, if the most recent non-missing measurement is obtained in triplicate), before the first dose of study drug on Day 1 of the Treatment Period.

Absolute change from baseline will be calculated as postbaseline value – baseline value.

Relative change from baseline will be calculated as (postbaseline value – baseline value)/baseline value.

Treatment-emergent (TE) period for Parts 1 and 3 will be from the first dose date of study drug in the Treatment Period until 28 days after the last dose date of study drug or end of study date (based on end of study visit in CRFs), whichever occurs first.

For Part 2, the TE period will be defined separately for the Run-In Period, and the Treatment Period:

The TE period for the Run-in Period will be from the first dose date of study drug in the Run-in Period to: (1) the first dose date of study drug in the Treatment Period for subjects who complete the Run-in Period and continue to the Treatment Period, or (2) 28 days after the last dose date of study drug in the Run-in Period or end of study date (based on end of study visit in CRFs), whichever occurs first, for subjects who do not continue to the Treatment Period (e.g., subjects who do not meet the criteria to enter the Treatment Period and re-enter Study 661-110). The TE period for the Treatment Period will be from first dose date of study drug in the Treatment Period to 28 days after the last dose date of study drug or end of study date (based on end of study visit in CRFs), whichever occurs first.

Unscheduled visits: Unscheduled visit measurements will be included in analysis as follows:

- In scheduled visit windows per specified visit windowing rules
- In the derivation of baseline and last on-treatment measurements
- In the derivation of maximum and minimum values during TE period, and maximum and minimum change from baseline values during TE period for safety analyses
- In individual subject data listings as appropriate

Visit windowing rules: The analysis visit windows for protocol-defined visits are provided in Appendix B.

Spirometry (ppFEV₁) will be used for both efficacy and safety purposes. For efficacy analysis, the assessments will follow the visit windowing rules for efficacy. For safety analysis, the assessments at pre-dose and 5 hours postdose on nominal days 1 and 15 will be used.

Incomplete/missing data will not be imputed, unless specified otherwise.

Outliers: No formal statistical analyses will be performed to detect or remedy the presence of statistical outliers, unless specified otherwise.

Multiplicity: There will be no multiplicity adjustment for performing multiple hypothesis tests, unless specified otherwise.

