8.2 Background Characteristics

8.2.1 Subject Disposition

For the Treatment Period in all Parts, subject disposition will be summarized as described below.

The number of subjects in the following categories will be summarized by treatment group and overall, for Parts 1 and 3:

- All Subjects Set (randomized or dosed)
- Randomized
- Safety Set
- Randomized but not dosed in Period 1 of the Treatment Period
- Full Analysis Set (FAS)

The number of subjects in the following categories will be summarized by treatment group and overall for Part 2:

- Randomized or dosed in the Period 1 of the Treatment Period
- Randomized
- Safety Set for the Treatment Period
- Randomized but not dosed in Period 1 of the Treatment Period
- Full Analysis Set (FAS)

The number and percentage (based on FAS) of subjects in each of the following disposition categories will be summarized by treatment group and overall:

- Completed study drug treatment (separately by Periods 1 and 2 for both Part 1 and Part 2)
- Prematurely discontinued treatment and the reason for discontinuation (i.e., discontinued all study drugs) (separately by Periods 1 and 2 for both Part 1 and Part 2)
- Completed study (i.e., completed Safety Follow-up Visit or completed all study drugs and re-entered Study 661-110 without Safety Follow-up per protocol)
- Prematurely discontinued the study and the reason for discontinuation

For the Run-in Period in Part 2, a separate disposition table will be provided with the following categories:

- Safety Set for the Run-in Period
- Enrolled but not dosed in the Run-in Period
- Completed treatment in the Run-in Period (i.e., completed randomization)
- Prematurely discontinued treatment during the Run-in Period and the reason for treatment discontinuation (i.e., discontinued all study drugs in the Run-in Period)

- Prematurely discontinued the study during the Run-in Period and the reason for study discontinuation

A listing will be provided by part, for subjects who discontinued treatment (including the Run-in Period in Part 2) or who discontinued study with reasons for discontinuation. A randomization listing of subjects will also be provided, by part.

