8.2.4 Study Drug Exposure

Study drug exposure (in days) will be calculated as: last dose date of study drug – first dose date of study drug + 1 day, regardless of study drug interruption, and will be summarized descriptively. Study drug exposure will be summarized for the overall study drug period, which includes the Treatment Period for Parts 1 and 3, and the Run-in Period and the Treatment Period for Part 2. Further, study drug exposure for the Treatment Period in Part 2 will also be summarized descriptively.

Study drug exposure (in weeks) will be summarized descriptively by the number of subjects (n), mean, SD, SE, median, min, and max. It will also be summarized in categories for Treatment Period: ≤ 2 weeks, $>2 - \leq 4$ weeks, and > 4 weeks (for Parts 1 and 3); and ≤ 2 weeks, $>2 - \leq 4$ weeks, $>4 - \leq 8$ weeks, >8 weeks (for Part 2), using counts and percentages. Additionally, the total study drug exposure, defined as the sum total of the study drug exposure across all subjects (in patient-weeks), will be provided.

Exposure summaries will be based on the Safety Set, and presented by treatment group and overall, for each part. For Part 2, exposure summaries will be based on the Safety Set for the Treatment Period.

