8.4.1 Adverse Events

For analysis purposes, AEs will be classified as pretreatment AEs, TEAEs, or post-treatment AEs, defined as follows:

For Parts 1 and 3:

Pretreatment AE: any AE that started before the first dose date of study drug

TEAE: any AE that worsened (either in severity or seriousness) or that was newly developed at or after the first dose date of study drug through the end of the TE period

Post-treatment AE: any AE that worsened (either in severity or seriousness) or that was newly developed beyond the TE period

For Part 2:

Pretreatment AE: any AE that started before the first dose date of study drug

TEAE during the Run-in Period: any AE that worsened (either in severity or seriousness) or that was newly developed at or after the first dose date of study drug through the end of the TE period for the Run-in Period

TEAE during the Treatment Period: any AE that worsened (either in severity or seriousness) or that was newly developed at or after the first dose date of study drug through the end of the TE period for the Treatment Period

Post-treatment AE: any AE that worsened (either in severity or seriousness) or that was newly developed beyond the TE period

For AEs with completely missing or partially missing start dates, if there is no clear evidence that the AEs started before or after study treatment, the AEs will be classified as TEAEs.

Details for imputing missing or partial start dates of adverse events are described in Appendix G.

AE summary tables will be presented for TEAEs only, for the TE period for Parts 1 and 3, or the TE period for the Treatment Period in Part 2, by treatment group and overall, for each part respectively, as applicable, for the following:

- Number of TEAEs (total number of TEAEs only)
- Subjects with any TEAEs
- Subjects with TEAEs by Strongest Relationship
- Subjects with TEAEs by Maximum Severity
- Subjects with TEAEs Leading to Study Drug Discontinuation (Discontinuation of all study drug)
- Subjects with TEAEs Leading to Study Drug Interruption (Interruption of all study drug)
- Subjects with Serious TEAEs
- Subjects with TEAE Leading to Death

Summaries will be presented by MedDRA SOC and PT using frequency counts and percentages (i.e., number and percentage of subjects with an event). When summarizing the number and

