8.4.2 Clinical Laboratory

For the treatment-emergent laboratory assessments, the observed values and change from baseline values of the continuous hematology, chemistry, and coagulation results will be summarized in SI units at each scheduled visit, by treatment group and part.

The number and percentage of subjects meeting at least 1 threshold analysis criterion event, during the TE period for Parts 1 and 3, or the TE period for Treatment Period for Part 2, will be summarized by treatment group and overall for each part. The threshold analysis criterion shift from baseline will also be summarized for selected laboratory parameters. The threshold analysis criteria are provided in [Appendix H](#).

For select LFT laboratory test (alanine transaminase [ALT], aspartate transaminase [AST], alkaline phosphatase [ALP], and total bilirubin), a scatter plot of the maximum treatment-emergent value versus the baseline value corresponding to \times ULN (upper limit of normal) will be presented. Further, a scatter plot of the maximum treatment-emergent value of ALT and AST, separately, versus the maximum treatment-emergent value of total bilirubin corresponding to \times ULN will also be presented by treatment group, for each part.

Results of abnormal urinalysis and positive urine/serum pregnancy test will be listed in individual subject data listings only.

In addition, a listing containing individual subject hematology, chemistry, and coagulation values outside the normal reference ranges will be provided. This listing will include data from both scheduled and unscheduled visits.

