8.4.5 Pulse Oximetry

For the treatment-emergent pulse oximetry measurements, a summary of observed values and change from baseline values will be provided at each scheduled visit, for the percent of oxygen saturation, by treatment group, for each part.

The number and percentage of subjects with shift changes from baseline (normal/missing and low according to the reference range) to the lowest percent of oxygen saturation during the TE Period for Parts 1 and 3, or the TE period for the Treatment Period in Part 2, will be summarized by treatment group and overall, for each part.

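### Part 2: TEAE incidence and threshold counts are planned only over the whole Treatment Period TE window, with no split at the Day 29 Visit, where VX-659 stops

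*SAP*

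**What the plan says.** Protocol Table 3-2 (dosing footnote) ends VX-659 in Part 2 with the morning dose at the Day 29 Visit, and TEZ/IVA with the morning dose at the Day 57 Visit. Protocol section 10 counts every component and every matching placebo as study drug, so Period 2 TEZ/IVA keeps the TE and exposure clocks running.

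SAP 8.1 opens the Part 2 window at first dosing with "study drug in the Treatment Period to 28 days after the last dose date of study drug or end of study date", whichever comes first. SAP 8.4 bases all Part 2 safety analyses on that window:

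- TEAE tables (8.4.1) use the plain TE window in the other two parts, "or the TE period for the Treatment Period in Part 2, by treatment group and overall, for each part respectively".
- Laboratory threshold counts (8.4.2) are taken "during the TE period for Parts 1 and 3, or the TE period for Treatment Period for Part 2". ECG (8.4.3) and vital signs (8.4.4) follow the same rule.
- Selected liver tests get "a scatter plot of the maximum treatment-emergent value versus the baseline value" (8.4.2).
- The oximetry shift table (8.4.5) runs from baseline "to the lowest percent of oxygen saturation during the TE Period for Parts 1 and 3", with the Treatment Period window as its Part 2 counterpart.

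On exposure, SAP 8.2.4 summarizes the Run-in plus Treatment Period, and adds that "study drug exposure for the Treatment Period in Part 2 will also be summarized descriptively". It also gives a total "defined as the sum total of the study drug exposure across all subjects (in patient-weeks".

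Other sections do separate the periods. Disposition (8.2.1) reports "Completed study drug treatment (separately by Periods 1 and 2 for both Part 1 and Part 2", and treatment discontinuation with its reason likewise. Compliance (8.2.5) is summarized for Period 1 only.

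**The concern.** Safety and tolerability of VX-659 in triple combination is a primary objective (Protocol 6.1). Part 2 is the only part in which VX-659 is compared with a control on a common TEZ/IVA background. In Part 2 the arms differ in VX-659 dosing only up to the Day 29 Visit, yet the incidence and extreme-value displays under the TC-high label pool that time with up to eight further weeks. No Period 1 version is specified. A reader who asks how many subjects had an event, or crossed a laboratory, ECG or vital-sign threshold, while the arms differed in dosing will find no table that answers. The by-visit summaries give values at visits, not counts of subjects with events or extremes.

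**Working it through.** **Inputs**

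- Last VX-659 dose: Day 29 Visit (±2 days). Last TEZ/IVA dose: Day 57 Visit (±3 days). Protocol Table 3-2.
- TE tail: 28 days after the last dose of any study drug. SAP 8.1.
- Exposure: last dose date − first dose date + 1. SAP 8.2.4.
- Run-in: 4 weeks (28 days). Protocol 9.1.2.
- About 27 subjects at 1:2, so 9 TEZ/IVA and 18 TC-high. Protocol Table 9-1.
- Event rates: the documents give none. Those used below are assumptions.

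**The plan's own figure.** 57 + 28 = Day 85, the Part 2 Safety Follow-up target day in SAP Table 11-4. It reproduces exactly.

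**What the window contains.** 85 = 29 (on VX-659) + 28 (Days 30–57) + 28 (Days 58–85).

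- On VX-659: 29/85 = 34%. Across the visit windows: 27/(60 + 28) = 31% to 31/(54 + 28) = 38%.
- Days 30–57 are what a 28-day tail applied to VX-659 alone would give. Only Days 58–85 go beyond it: 28/85 = 33%.
- For re-entry to Study 661-110 without a Safety Follow-up Visit (Protocol 9.1.5), the window ends at about Day 57. Then 29/57 = 51% is on VX-659 and Days 58–85 do not exist.
- Part 1: 33 + 28 = Day 61; 29/61 = 48%, with 4 days beyond the tail. Part 3: 29 + 28 = Day 57; 29/57 = 51%, with none. The point is specific to Part 2.

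**Exposure of a nominal TC-high completer.** Treatment Period: 57 days, 57/7 = 8.1 weeks. With Run-in: 28 + 57 = 85 days, 12.1 weeks. VX-659: 29 days, 4.1 weeks. For 18 completers: 18 × 57/7 = 146.6 patient-weeks of study drug, of which 18 × 29/7 = 74.6 include VX-659.

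**Illustration with assumed rates.** Let incidence be 30% (TC-high) and 10% (control) in Period 1, then b per 4-week block in both arms. After k further blocks, incidence = 1 − (1 − p)(1 − b)^k. With b = 10%:

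| Window | TC-high | Control | Risk ratio | Difference (points) |
|---|---|---|---|---|
| Period 1 | 30.0% | 10.0% | 3.0 | 20.0 |
| To Day 57 | 37.0% | 19.0% | 1.95 | 18.0 |
| To Day 85 | 43.3% | 27.1% | 1.60 | 16.2 |

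- The step due to Days 58–85 is 1.95 to 1.60. With b = 5% it is 2.31 to 1.96, and with b = 20% it is 1.57 to 1.30.
- The whole shift in the difference is 3.8 points, or 0.68 of 18 subjects and 0.34 of 9.
- If TC-high keeps half its excess during washout (20% against 10% in Days 30–57, then 10% in both arms), the ratios are 3.0, 2.32 and 1.83, but the differences are 20.0, 25.0 and 22.5 points. The full window then shows the larger absolute difference.
- With 9 controls at 10%, the chance of no control event in Period 1 is 0.9^9 = 39%, which leaves the ratio undefined. Over the full window it is 0.729^9 = 6%.

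**The case against.** The plan has a good defence, and much of it stands.

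- **The SAP follows the protocol.** Protocol 12.3.1 defines one TE Period from the first Period 1 dose, tied to the last dose of study drug, and 12.3.5 bases all safety analyses on it. SAP 2.1 discloses its change to the end rule. Both arms share the window, so the comparison remains randomized. This stands.
- **Follow-up after VX-659 is legitimate.** Period 2 is the VX-659 washout, and delayed events belong in a safety table. This stands for Days 30–57, and is why the full-window tables must stay.
- **On-VX-659 safety is not confined to listings.** A reader might infer that it is. Laboratory, ECG, vital-sign and oximetry values are summarized by arm at Days 15 and 29, post-dose spirometry at Days 1 and 15, and discontinuation by period. This narrows the gap to incidence and extreme-value counts but does not close it.
- **The exposure section is not wrong.** A reader might infer that it credits TC-high with twice its VX-659 exposure. SAP 8.2.4 defines study drug exposure and says so, and the TEAE tables use percentages of subjects, not patient-weeks. What remains is that a reader cannot take the 57 or 85 days as VX-659 exposure.
- **A Period 1 table is the less stable one**, with about 9 controls. True; it supplements the full-window table.
- **Other displays may exist.** The IDMC SAP named in SAP 9.2 is not available here and may hold by-period tables. It would not supply them to the final analysis, which this SAP governs.

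**Conclusion.** The point holds as a low-cost improvement to the Part 2 safety presentation. TEAE incidence, threshold counts, the liver-test plots and the oximetry shift table are planned only over a window of nominally 85 days, of which 29 are on VX-659 and 28 lie beyond ordinary follow-up of it. That last block is absent for re-entrants to Study 661-110, whose number the documents do not give. The day counts assume completers on nominal visit days.

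A reader might infer that the TE definition is an error, or that the full window must hide a VX-659 effect. The documents support neither. The definition agrees with the protocol, safety is descriptive, and no test or decision rule depends on it. The dilution figures rest on assumed rates, move the difference by less than one subject per arm, and can reverse in direction for absolute risk if the excess persists into washout. Equal event rates in the two arms from Day 30 are not established. The case for the split is that it shows when events occurred, whichever way they fall.

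**What to change.** Leave the TE definition and all full-window tables as they are.

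1. **SAP 8.4, Part 2:** add supplementary TEAE and threshold tables (laboratory, ECG, vital signs) split by date of onset or measurement. The first window runs from the first Day 1 dose through the calendar date of the Day 29 Visit. If that visit is missed or treatment stopped early, it runs through study Day 29, or to end of study if sooner. The second window runs from the next day to the end of the TE period. Use dates only and the same rule in both arms. Day 29 safety assessments are predose and fall in the first window. Footnote that a subject with events in both windows counts in each, so the columns need not add up to the full-window count.
2. **SAP 8.2.4, optional:** add a Part 2 line for Period 1 (VX-659 or matching placebo) exposure. Give days as well as weeks, because on-window Day 29 Visits (27–31 days, 3.9–4.4 weeks) straddle the 4-week category limit.

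The cost is a few lines of SAP text and a date-filtered rerun of existing programs. The downside is one more table set for about 27 subjects, with ratios that should not be over-read.
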